The primary endpoint of Part 3 is the ORR, defined as the percentage of patients with a confirmed PR or better (ie, PR, VGPR, CR, and sCR) according to the IMWG Response Criteria (Appendix F) assessed by the independent review committee (IRC). The primary endpoint, ORR assessed by IRC, will be evaluated for all treated patients within each treatment arm based on the 95% exact confidence interval (CI) of the observed ORR at the primary analysis. No formal statistical analysis will be performed to compare the 2 treatment arms. Prespecified subgroup analyses based on stratification factors will be performed as data permits.

Two interim analyses for futility are planned for the study when approximately 15 and 48 of the planned 118 patients per arm have been randomized and treated for at least 3 cycles or discontinued treatment prematurely. The futility stopping boundary is determined based on the predictive probability of success (Lee and Liu 2008) at the primary analysis. The treatment arm will be dropped for futility if the predictive probability of success at the primary analysis is found to be smaller than 10% based on the data from the interim analysis.

Two-sided exact 95% binominal CIs will be computed for all binary secondary endpoints, including ORR as assessed by the investigator, DCR, and CBR as assessed by the IRC and the investigator. Kaplan-Meier methods, including medians and CIs, will be used to estimate PFS as assessed by the IRC and the investigator, DOR as assessed by the IRC and the investigator, OS, and other time to event endpoints.

Sample Size Justification

Part 1 of the study will follow a standard 3 + 3 dose escalation design. MTD/OBD will be defined for each schedule currently under evaluation (B [Q2W], C [Q3W] and D [Q4W]). A maximum of 9 dose levels are planned (from 0.001 mg/kg to 14 mg/kg). For Part 1, the number of evaluable patients is planned to be 36 to 51.

Part 2 Expansion:

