The study will enroll up to 25 patients in each Part 2 cohort to further characterize safety of the OBD/MTD and obtain preliminary clinical efficacy data. An OBD/MTD dose will be considered clinically relevant if at least 11 out of 25 response-evaluable patients have a confirmed PR or better. With a vague beta prior with shape parameters 0.428 and 1 for ORR, 11 responders out of 25 gives a greater than 90% posterior probability of true ORR being greater than 30%. The design has reasonable operating characteristics. With a true ORR of 30%, the probability of declaring success is 7%. On the other hand, with a true ORR of 50% the probability of declaring success is 70%.

Part 3 Extension:

A total sample size of approximately 236 patients (118 patients per arm) will allow the study to have over 90% power to rule out an uninteresting response rate of 20% if the true rate is 35% with a 1-sided alpha of 0.025. Patients who were randomized but did not receive any study treatment will be replaced. However, all patients who received at least one dose of study treatment will be included in the analysis and will not be replaced if they drop out after receiving study treatment.

After global patient enrollment is completed in Part 3, enrollment will continue for the China continuation cohort until about 15% of the total sample size is reached at the selected dose(s) (eg, 18 patients based on 118 patients treated at the selected dose[s]).

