The modakafusp alfa doses of 1.5 and 3 mg/kg Q4W will be translated into 2 fixed doses of 120 and 240 mg based on the median bodyweight of approximately 80 kg (from Parts 1 and 2 of Study TAK-573-1501) for the Part 3 evaluation.

Two interim analyses for futility are planned for the study when approximately 15 and 48 patients of the planned 118 patients per arm are enrolled and treated for at least 3 cycles or have discontinued treatment prematurely (Figure 6.b).

The sponsor will only proceed with enrolling additional patients into a treatment arm where the futility boundary is not crossed; more specifically:

Scenario 1: If the futility boundary is not crossed in one arm (eg, the 120 mg arm) but is crossed in the second treatment arm (eg, the 240 mg arm), patient enrollment will continue only in the arm that did not cross the futility boundary (eg, the 120 mg arm).

Scenario 2: If the futility boundary is not crossed in the 120 mg treatment arm and is not crossed in the 240 mg treatment arm, patient enrollment will continue for both arms to identify the optimal dose, defined as having the more favorable risk-benefit profile based on the totality of data from both arms and Parts 1 and 2.

Scenario 3: If the futility boundary is crossed in the 120 mg treatment arm and is crossed in the 240 mg treatment arm, the study will be terminated.

[figure not shown]
In addition, the sponsor may decide to discontinue 1 arm if there is early detection of an unfavorable risk-benefit profile based on the interim data analysis data.

Study procedures and assessments, with their time points, are shown in Appendix A, Appendix B, and Appendix C.

Part 3 China Continuation Cohort

After global patient enrollment is completed in Part 3, enrollment will continue for the China continuation cohort until about 15% of the total sample size is reached at the selected dose(s) (eg, 18 patients based on 118 patients treated at the selected dose[s]).

Figure 6.b Part 3 Study Schematic

PD: progressive disease; Q4W: once every 4 weeks. Dosing is Q4W in both cohorts.

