13.2.2 Part 3 Extension

13.2.2.1 Part 3 Futility Stopping Rules

Two interim analyses for futility are planned for the Part 3 extension cohorts when approximately 15 and 48 patients of the planned 118 patients per arm are enrolled and treated for at least 3 cycles or have discontinued treatment prematurely. The futility stopping boundary will be determined based on the predictive probability of success at the primary analysis, using a Bayesian efficacy monitoring approach (Lee and Liu 2008). The treatment arm will be dropped for futility if the predictive probability of success at the primary analysis is found to be <10% based on the data from the interim analysis. Various prior distributions for the ORR are used for each treatment arm due to different prior efficacy information at different dose levels collected in Parts 1 and 2 of the study. To reflect the prior efficacy information for the 120 mg arm (40% ORR) collected in Parts 1 and 2, a weakly informative prior of Beta (1.2, 1.8) is used. However, because of comparatively limited efficacy data available at the 3 mg/kg (240 mg) dose, a noninformative prior of Beta (0.5, 0.5) is used. Based on these prior distributions, Table 13.a shows the stopping rules used for the treatment arms of 240 mg and 120 mg at each interim futility analysis. The details of the operating characteristics of the futility stopping rules are described in Appendix H.

There is no plan to stop for efficacy based on the interim analysis data.

Table 13.a Stopping Boundaries for 240 and 120 mg Arms at Each Interim Futility Analyses

	Number of patients enrolled and followed up	Recommend terminating the corresponding treatment arm due to lack of efficacy when number of responders is:			
for 3 month		240 mg Arm	120 mg Arm		
1st Interim Futility Analysis	15	≤2	≤1		
2 nd Interim Futility Analysis	48	≤10	≤10		

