13.3 Determination of Sample Size

Part 1 of the study will follow a standard 3 + 3 dose escalation design. Under this design, the probability of dose escalation according to the true DLT rate is as follows:

True DLT rate	5%	10%	20%	30%	40%	50%	60%	70%
Probability of escalating	97%	91%	71%	49%	31%	17%	8%	3%

DLT: dose-limiting toxicity.

The probability of not observing a DLT in a sample size of 6 patients according to the true DLT rate is as follows:

True DLT rate	5%	10%	20%	30%	40%	50%	60%	70%
Probability of no toxicity	74%	53%	26%	12%	4.7%	1.6%	0.4%	<0.1%

DLT: dose-limiting toxicity.

Patients will be considered evaluable in Part 1 for MTD/OBD assessment provided they have not missed any of their infusions of modakafusp alfa in Cycle 1 and have not had a DLT. Patients who are not considered evaluable as defined above will be replaced.

Part 2 Expansion

The study will enroll up to 25 patients in each arm to further characterize safety of the OBD/MTD and obtain preliminary clinical efficacy data. An OBD/MTD dose will be considered clinically relevant if at least 11 out of 25 response evaluable patients have a confirmed PR or better. With a vague beta prior with shape parameters 0.428 and 1 for ORR (ie, mean of 30%), 11 responders out of 25 gives a greater than 90% posterior probability of true ORR being greater than 30%. The design has reasonable operating characteristics. With a true ORR of 30%, the probability of declaring success is 7%. In contrast, with a true ORR of 50%, the probability of declaring success is 70%.

Part 3 Extension

The primary objective of Part 3 of the study is to determine the confirmed ORR, including PR, VGPR, CR, and sCR assessed according to the IMWG criteria (Appendix F) to modakafusp alfa in patients with MM previously treated with ≥3 lines and with evidence of disease progression who are refractory to, or intolerant of, a PI, an IMiD, and an anti-CD38 mAb (triple refractory). The sample size was determined to claim that the true ORR is greater than the threshold response rate of 20% within each treatment arm. A total sample size of approximately 236 enrolled patients (118 patients per arm) will allow the study to have over 90% power to rule out an uninteresting response rate of 20% if the true rate is 35% with a 1-sided alpha of 0.025.

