6.0 DETERMINATION OF SAMPLE SIZE

Part 1 of the study will follow a standard 3+3 dose escalation design. Under this design, the probability of dose escalation according to the true DLT rate is as follows:

True DLT rate	5%	10%	20%	30%	40%	50%	60%	70%
Probability of escalating	97%	91%	71%	49%	31%	17%	8%	3%

DLT: dose-limiting toxicity.

The above probability is calculated by summing up the probability of the two below events that leads to dose-escalation:

- a) no DLT in the first cohort of 3 patients at a dose level, or
- b) One DLT in the first cohort of 3 patients and no DLT in the second cohort of 3 patients at a dose level.

The probability of not observing a DLT in a sample size of 6 patients according to the true DLT rate is as follows:

True DLT rate	5%	10%	20%	30%	40%	50%	60%	70%
Probability of no toxicity	74%	53%	26%	12%	4.7%	1.6%	0.4%	<0.1%

DLT: dose-limiting toxicity.

Patients will be considered evaluable in phase 1 for MTD/OBD assessment provided that they have not missed any of their infusions of modakafusp alfa in Cycle 1 or have had a DLT. Patients who are not considered evaluable as defined above will be replaced.

Part 2 Expansion

The number of patients in the dose expansion phase was determined based on a binomial exact test design. A sample size of 25 patients will allow a cohort to have over 80% power to rule out an uninteresting response rate of 10% if the true response rate is 30% with a one-sided alpha of 0.05. A Bayesian predictive probability design is used to allow multiple interim analyses to stop early for futility. The study will enroll up to 25 patients in each cohort to further characterize safety of the OBD/MTD and obtain preliminary clinical efficacy data. With a vague beta prior with shape parameters 0.428 and 1 for ORR (i.e., mean of 30%), 11 responders out of 25 gives a greater than 90% posterior probability of true ORR being greater than 30%. An OBD/MTD dose will be considered clinically relevant if 11 out of 25 response evaluable patients have a confirmed PR or better. The design has reasonable operating characteristics. With a true ORR of 30%, the probability of declaring success is 7%. In contrast, with a true ORR of 50%, the probability of declaring success is 70%.

See Section 7.13 for details of futility analyses after 10 and 15 evaluable patients are enrolled in the expansion phase.

Part 3 Extension

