The primary objective of Part 3 of the study is to determine the confirmed ORR, including PR, VGPR, CR, and sCR assessed according to the IMWG criteria to modakafusp alfa in patients with MM previously treated with ≥ 3 lines and with evidence of disease progression who are refractory to, or intolerant of, a PI, an IMiD, and an anti-CD38 mAb (triple refractory). The sample size was determined to claim that the true ORR is greater than the threshold response rate of 20% within each treatment arm. A total sample size of approximately 236 enrolled patients (118 patients per arm) will allow the study to have over 90% power to rule out an uninteresting response rate of 20% if the true rate is 35% with a 1-sided alpha of 0.025.

The purpose of the China continuation cohort is to allow continued evaluation of efficacy and any emerging safety signals in Chinese patients enrolled in China. After global patient enrollment is completed in Part 3, enrollment will continue for the China continuation cohort until about 15% of the total sample size is reached at the selected dose(s) (eg, 18 patients based on 118 patients treated at the selected dose[s]).

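### Does the Part 3 claim of over 90% power conflict with the 89% probability of success printed for the 240 mg arm?

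*Protocol*

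**What the plan says.** Protocol 13.3 sets the target arm by arm: "The sample size was determined to claim that the true ORR is greater than the threshold response rate of 20% within each treatment arm". It then gives the power for 236 patients at one-sided alpha 0.025: "118 patients per arm) will allow the study to have over 90% power to rule out an uninteresting response rate of 20"%. Protocol 2.0 says that this sample "will allow the study to have over 90% power to rule out an uninteresting response rate of 20% if the true rate is 35"%, and SAP 6.0 that it "will allow the study to have over 90% power to rule out an uninteresting response rate of 20"%. None of these sentences mentions futility stopping.

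The looks are described elsewhere. Protocol 2.0, Statistical Considerations, places them "when approximately 15 and 48 of the planned 118 patients per arm have been randomized" and treated for at least 3 cycles or discontinued early. Protocol 13.2.2.1 gives the rule: "The treatment arm will be dropped for futility if the predictive probability of success at the primary analysis is found to be <10"%. Table 13.a turns this into counts: 2 or fewer of 15 (240 mg) or 1 or fewer of 15 (120 mg), then 10 or fewer of 48 in either arm. Protocol 13.2.2.1 points to Appendix H, and SAP 7.13 to SAP Appendix D. Both appendices define success as at least 33 responders of 118. At a true rate of 35% they print a probability of success of 89% (240 mg) and 93% (120 mg).

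**The concern.** A reader normally takes the design power from the sample-size section. Here that section gives one unqualified figure for a per-arm claim, while the appendix to the same document gives a figure just below it for one arm. If the stopping rule is part of the design, the 240 mg arm appears not to reach its advertised power, and the sample-size text appears to overstate what the trial can do. SAP 6.0 adds to the impression of an oversight: its Part 2 text carries a pointer, "See Section 7.13 for details of futility analyses after 10 and 15 evaluable patients are enrolled in the expansion phase", and its Part 3 text has none. At stake would be the accuracy of the stated power and, had the gap been large, whether 118 per arm is enough.

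**Working it through.** **Inputs.** Null rate 0.20, alternative 0.35, one-sided alpha 0.025 and N = 118 per arm (Protocol 13.3, SAP 6.0). Success at 33 or more responders (Protocol Appendix H, SAP Appendix D). Boundaries, priors Beta(0.5, 0.5) for 240 mg and Beta(1.2, 1.8) for 120 mg, and the 10% threshold (Protocol 13.2.2.1, SAP 7.13).

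**1. Success cutoff.** The exact lower 95% limit for r responders of 118 is the 0.025 quantile of Beta(r, 118 − r + 1). It is 0.1935 at r = 32 and 0.2010 at r = 33, so 33 is the smallest count that excludes 20%. The type I error is P(X ≥ 33 | 118, 0.20) = 0.0235.

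**2. The plan's stated power, fixed sample.** P(X ≥ 33 | 118, 0.35) = 0.9573. Over 90% is correct, with 95.7 − 90 = 5.7 points to spare.

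**3. Boundaries.** Beta-binomial predictive probability of reaching 33 of 118:

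| Arm | First look, stop | First look, continue | Second look, stop | Second look, continue |
|---|---|---|---|---|
| 240 mg | 2/15: 8.8% | 3/15: 24.9% | 10/48: 8.7% | 11/48: 17.6% |
| 120 mg | 1/15: 3.1% | 2/15: 11.7% | 10/48: 9.7% | 11/48: 18.9% |

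The printed boundaries follow from the 10% rule.

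**4. Probability of success with binding looks, true rate 0.35.** Take the binomial distribution for 15 patients and remove the stopped counts. Convolve with 33 more patients and remove again. Convolve with the last 70 and sum from 33 upward. First-look stopping can be checked by hand:

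- 240 mg: P(X ≤ 2 | 15, 0.35) = 0.00156 + 0.01262 + 0.04756 = 0.0617
- 120 mg: P(X ≤ 1 | 15, 0.35) = 0.00156 + 0.01262 = 0.0142

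| Arm | Stopped by look 1 | Stopped by look 2 | Success | Printed in the appendices |
|---|---|---|---|---|
| 240 mg | 0.0617 | 0.0769 | 0.8944 | 6%, 8%, 89% |
| 120 mg | 0.0142 | 0.0356 | 0.9322 | 1%, 4%, 93% |

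The appendices are reproduced. Futility stopping costs 0.9573 − 0.8944 = 0.0629 in the 240 mg arm and 0.9573 − 0.9322 = 0.0251 in the 120 mg arm. Against 90%, the 240 mg gap is 0.9000 − 0.8944 = 0.0056, or 0.6 points.

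**5. How firm the 0.6 points is.** The looks are at approximately 15 and 48, and SAP 7.13 recalculates the boundaries at the observed numbers. For 240 mg the first boundary is 1 for 10 to 14 patients and 2 for 15 to 19, so the planned look sits exactly on a step. With the second look held at 10/48:

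| First look, n | 12 | 13 | 14 | 15 | 16 | 17 | 18 | 19 |
|---|---|---|---|---|---|---|---|---|
| 240 mg success | 90.9% | 92.0% | 92.7% | 89.4% | 90.9% | 91.9% | 92.6% | 93.1% |

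Earlier first looks, at 10 and 11, give 87.1% and 89.3%. Moving both looks gives 93.2% at 14 and 46, and 91.3% at 16 and 50. With the first look at 15 and the second anywhere from 45 to 51, the result is 89.4% to 90.0%. Over first looks at 10 to 19 with the second at 10/48, the 120 mg arm stays between 90.9% and 93.5%. Under the planned looks, the 240 mg arm reaches 90% at a true rate of 35.2%.

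**The case for a change.** The best argument for a change is that the stopping rule is not optional. Protocol 6.1 says: "The sponsor will only proceed with enrolling additional patients into a treatment arm where the futility boundary is not crossed". The appendices themselves treat the boundaries as binding, and the sample-size claim is explicitly per arm. On that reading the design's probability of success for 240 mg at its planned looks is 89%, and a statement of over 90% does not describe it. Disclosure in an appendix does not reconcile the two places, the Part 2 text shows that the authors knew how to cross-refer, and a few words would settle it.

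Most of this is factually right. The Part 3 power sentences carry no label, and 15 is the planned look, so the shortfall cannot be waved away as an unlikely case. Three things limit its force. The appendix figure has its own name and sits among the operating characteristics of the futility rules, so the documents report two correct numbers for two quantities. The binding reading is not the only one: Table 13.a words a crossing as a recommendation, and if crossings were not acted on, the 240 mg figure would lie between 89.4% and 95.7%. Finally, Protocol 13.2.2.1, with its pointer to Appendix H, comes shortly before 13.3, and Protocol 2.0 describes the looks just ahead of its power sentence.

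**Conclusion.** No change to the plan is needed. The power statement is true for the fixed sample of 118 per arm (95.7%), and the futility-adjusted figures of 89% and 93% are correct and printed in both documents. The gap is one of labelling: 0.6 points against 90%, in one arm, on the binding reading at the planned looks. It disappears for first looks at 12 to 14 or 16 to 19 patients with the second look at 10/48. An analyst or assessor who needs the adjusted power will find it in the appendix, and nothing in the conduct, the stopping decisions, the success criterion or the reported response rates depends on which figure the sample-size paragraph carries.

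The calculation assumes independent patients with a common true rate of 35%, and the same responder status at the interim and at the primary analysis. The printed tables are reproduced on that basis. SAP 7.8.2.1 uses a computer algorithm at the interims and the independent review committee for the primary endpoint, so disagreement between the two, or responses that emerge after an interim, would move the adjusted figures. That would not affect the fixed-sample statement.

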14.0 QUALITY CONTROL AND QUALITY ASSURANCE

14.1 Study-Site Monitoring Visits

Monitoring visits to the study site will be made periodically during the study to ensure that all aspects of the protocol are followed. If monitors are not allowed to perform on-site visits for data verification due to exceptional circumstances (eg, COVID-19), remote electronic medical records access visits may be conducted (where allowed by local laws and regulations). Source documents will be reviewed for verification of data recorded on the eCRFs. Source documents are defined as original documents, data, and records. The investigator and institution guarantee access to source documents by the sponsor or its designee (CRO) and by the IRB or IEC.

All aspects of the study and its documentation will be subject to review by the sponsor or designee (as long as blinding is not jeopardized), including but not limited to the Investigator's Binder, study medication, subject medical records, informed consent documentation, documentation of subject authorization to use personal health information (if separate from the ICFs), and review of eCRFs and associated source documents. It is important that the investigator and other study personnel are available during the monitoring visits and that sufficient time is devoted to the process.

14.2 Protocol Deviations

The investigator should not deviate from the protocol, except where necessary to eliminate an immediate hazard to study subjects. Should other unexpected circumstances arise that will require deviation from protocol-specified procedures, the investigator should consult with the sponsor or designee (and IRB or IEC, as required) to determine the appropriate course of action. There will be no exemptions (a prospectively approved deviation) from the inclusion or exclusion criteria.

The site should document all protocol deviations in the subject's source documents. In the event of a significant deviation, the site should notify the sponsor or its designee (and IRB or EC, as required). Significant deviations include, but are not limited to, those that involve fraud or misconduct, increase the health risk to the subject, or confound interpretation of primary study assessment.

The sponsor will assess any protocol deviation; if it is likely to affect to a significant degree the safety and rights of a subject or the reliability and robustness of the data generated, it may be reported to regulatory authorities as a serious breach of GCP and the protocol.

14.3 Quality Assurance Audits and Regulatory Agency Inspections

The study site also may be subject to quality assurance audits by the sponsor or designees. In this circumstance, the sponsor-designated auditor will contact the site in advance to arrange an auditing visit. The auditor may ask to visit the facilities where laboratory samples are collected, where the medication is stored and prepared, and any other facility used during the study. In addition, there is the possibility that this study may be inspected by regulatory agencies, including those of foreign governments (eg, the US FDA, the United Kingdom Medicines and Healthcare products Regulatory Agency, the Pharmaceuticals and Medical Devices Agency of Japan). If the study site is contacted for an inspection by a regulatory body, the sponsor should be notified immediately. The investigator and institution guarantee access for quality assurance auditors to all study documents as described in Section 14.1.

